## 10.7.2. Secondary endpoint analysis

The secondary objectives are to compare safety laboratory and ECG data among the acoziborole and placebo groups. Data will be analysed using double delta analysis versus

baseline and will use time, age- and sex-matched comparisons.

The secondary endpoints are the occurrence of AEs from the time that subjects provide written informed consent to the EoS and changes from baseline in ECG and laboratory safety test results (biochemistry and haematology) to the EoS.

The majority of measured parameters are quantitative and the change from baseline will be the difference between two values. For parameters with binary outcomes (presence or absence), contingency tables (before versus after treatment) will describe the change (or not) of status.

No adjustment for multiplicity of symptoms or laboratory results is planned. The results will therefore not be confirmatory but considered as a signal of potential effect.

#### Analysis of ECG:

- ECG parameters and changes from baseline ( $\Delta$ ) at D5 will be summarised by treatment group
- Placebo-corrected change from baseline (ΔΔ) will be calculated for each parameter using an analysis of covariance model
- Correlation between ΔQTc and acoziborole concentrations in blood at D5 will be investigated though linear or non-linear regression approaches.
- Incidence of ECG parameters meeting predefined thresholds for abnormality (absolute values of  $\Delta$ ) or of ECG presenting morphological abnormality will be computed by treatment group.

#### Subset of subjects for ECG Analysis:

- To characterise the effect of acoziborole on QTc prolongation, manually measured intervals from digitalised triplicate ECG will be used.
- Triplicate ECG measurements will be collected and stored for all subjects, but the analysis will be performed on the ECG data of the first 192 subjects, who received at least one tablet of acoziborole or placebo and have valid ECG evaluations
- According to previous studies performed with acoziborole either on healthy volunteers or HAT patients, a common SD of 12 msec and a maximum expected difference with placebo of 4 msec were assumed. The 192 subjects (accounting for the randomisation block size of 16 subjects) will ensure a power above 90% to demonstrate that the effect of acoziborole on QTc is below the threshold of regulatory concern ( $\Delta\Delta$ QTc 90% upper bound <10 msec).
- If this criteria of no QTc prolongation is reached, other ECG collected will not be analysed, otherwise the ECG for remaining subjects will be analysed and the effect of acoziborole on QTc prolongation will be estimated at completion of the study.
- In any case, the investigators will review the automatic ECG printouts for safety evaluation during the study.

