## 2.2.2. Secondary endpoint(s)

- Occurrence of adverse events (AEs) from ICF signature to the EoS
- Change from baseline in ECG parameters, biochemistry and haematology
- Blood concentration of acoziborole at Day 5 and Month 1
- ΔQTc measurements at Day 5
- Placebo-corrected change from baseline in ECG parameters (double delta [ΔΔ] heart rate [HR], ΔΔRR, ΔΔPR, ΔΔQRS, ΔΔQT and ΔΔQTc)
- Incidence of abnormal values and morphological findings in ECG at Day (D)5

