### 7.7. Blinding and procedures for unblinding

#### 7.7.1. Blinding Measures

Investigators, personnel of the clinical sites, the Sponsor (including biostatistics and data management personnel and the study monitors), and the participants will remain blinded during the study (i.e. until database lock). To ensure the double blind conditions of the study, acoziborole and matching placebo tablets will be identical in appearance. The packaging and labelling will be designed to maintain blinding of the Sponsor, study personnel and the subjects. The study data will remain blinded until the study database lock, and authorisation of data release according to standard operating procedures.

The randomisation list will be generated by Creapharm (packaging and labelling service providers) by respecting the ratio 3:1 using blocks of 16 kits.

The randomisation list is kept at Creapharm, who was in charge of assigning the kit number for the replacement of the 8 first subjects lost to follow-up.

Randomization data will be kept strictly confidential until the time of final database lock and will not be accessible by anyone else involved in the study, with the following exceptions:

- SGS, the bioanalyst for PK analysis (to avoid the unnecessary analysis of placebo samples)
- The independent statistician from PhinC, who will be in charge of analysing the correlation between ECG measurements and acoziborole concentrations at Day 5
- The designated person from DNDi Pharmacovigilance (or delegate), who will be in charge of unblinding of suspected unexpected serious adverse reaction (SUSARs) in case of exceptional request from the Health Authorities for regulatory safety reporting.
- The designated DNDi unblinded statistician, who will receive a scratching list to be used for individual unblinding in case of request from DSMB members

To ensure maintenance of the blinding during the study, a specific analytical code for PK and ECG analysis will be generated.

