#### Table 4. Schedule of ECG recordings

Ideal timing of ECG recordings	Acceptable time window
(after 20-minute rest interval and before PK sampling)	Acceptable time window

Day 1: before intake of IP	within 1.5 hour before intake of IP
Day 5: 96 hours after intake of IP	± 1 hour

ECG=electrocardiogram; IP=investigational product; PK=pharmacokinetic.

Electrocardiogram for all subjects will be collected but only data from the first 192 subjects administered with the study drug and who have a valid ECG and a PK sample at D5, will be analysed to assess effect of acoziborole versus placebo at D5. If any signal is detected in this first analysis, all ECG collected will be then analysed. If no signal is detected, ECGs collected for other subjects will be used for safety documentation purposes.

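### Two different triggers decide whether the ECGs of the 1,008 subjects beyond the first 192 are analysed, and they conflict when mean QTc passes but another ECG endpoint shows a signal

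*Protocol*

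**What the plan says.** Protocol section 8.3.6 (text under Table 4) collects ECGs from everyone and analyses the first 192 subjects for the effect of acoziborole against placebo at Day 5. It then states: "If any signal is detected in this first analysis, all ECG collected will be then analysed". Without a signal, the other tracings are kept as safety documentation. The word signal is not defined.

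Section 10.7.2, under the heading on the ECG subset, also starts from the first 192 but applies a narrower rule. The criterion is a placebo-corrected change with "QTc 90% upper bound <10 msec", and "If this criteria of no QTc prolongation is reached, other ECG collected will not be analysed". If the criterion fails, the remaining ECGs are analysed and the effect on QTc is estimated at study completion. The same section adds: "In any case, the investigators will review the automatic ECG printouts for safety evaluation during the study".

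The secondary endpoints in section 2.2.2 go beyond QTc. They include placebo-corrected changes in heart rate, RR, PR, QRS and QT, and "Incidence of abnormal values and morphological findings in ECG at Day (D)5". Neither section 2.2.2 nor the ECG analysis bullets in 10.7.2 limit that last endpoint to the subset.

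The two sections also define the 192 differently. Sections 8.3.4 and 8.3.6 require a valid ECG and a Day 5 PK sample; section 10.7.2 requires a valid ECG only. SAP section 5.2.5 defers the ECG analysis to a separate document, which was not available for this review.

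**The concern.** Suppose the first 192 subjects meet the QTc criterion, but acoziborole shows PR or QRS prolongation, an excess of values beyond the predefined thresholds, or new morphological findings. Section 8.3.6, read plainly, sends all stored ECGs to analysis. Section 10.7.2 stops at 192. This case is foreseeable, because the protocol names those measures as endpoints.

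Under section 10.7.2, a test on mean QTc alone decides whether further data are examined for endpoints on which that test is silent. Following it as written would leave a non-QTc signal from 192 subjects without follow-up in the tracings already collected from the other 1,008. Day 5 is the only scheduled post-dose ECG, so no later scheduled tracing would fill the gap.

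**Working it through.** **Inputs.** Section 10.7.2: "a common SD of 12 msec and a maximum expected difference with placebo of 4 msec were assumed"; margin 10 msec on the upper bound of a 90% interval (one-sided 5%); "The 192 subjects (accounting for the randomisation block size of 16 subjects) will ensure a power above 90" per cent. Section 7.7.1: allocation "by respecting the ratio 3:1 using blocks of 16 kits". Section 10.1.1: 900 acoziborole and 300 placebo.

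**Subset size.** 192 / 16 = 12 blocks. At 3:1 that is 192 × 3/4 = 144 acoziborole and 48 placebo. Outside the subset are 1,200 − 192 = 1,008 subjects: 900 − 144 = 756 acoziborole and 300 − 48 = 252 placebo.

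**The stated power reproduces.** SE = 12 × √(1/144 + 1/48) = 2.00 msec. Power = Φ((10 − 4)/2.00 − 1.645) = Φ(1.355) = 91.2% (91.1% with the noncentral t). The subset is adequate for the purpose it was sized for.

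**What passing means.** The bound is below 10 msec when the observed mean difference is below 10 − 1.645 × 2.00 ≈ 6.7 msec. This is a condition on the QTc mean only.

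**The two rules side by side.**

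| Result in the first 192 | Section 8.3.6 | Section 10.7.2 |
|---|---|---|
| QTc criterion fails | Analyse all (if this counts as a signal) | Analyse all |
| QTc met, no other signal | Stop at 192 | Stop at 192 |
| QTc met, signal in HR, PR, QRS, outliers or morphology | Analyse all | Stop at 192 |

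Only the third row is in conflict.

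**Can the third row occur?** The documents give no rate of ECG outliers, so this is an illustration on assumed figures. Let a fraction f of exposed subjects have a 60 msec QTc prolongation and the rest no effect, with SD 12 msec (20,000 simulated trials per row). The mean shift is 60 × f; the chance that at least one such subject is among the 144 is 1 − (1 − f)^144.

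| f | Mean shift (msec) | QTc criterion met | At least one among 144 |
|---|---|---|---|
| 1% | 0.6 | 99.6% | 76.5% |
| 2% | 1.2 | 98.5% | 94.5% |
| 3% | 1.8 | 96.1% | 98.8% |
| 5% | 3.0 | 83.9% | 99.9% |

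So outliers can be present in the first 192 while the criterion is comfortably met, even for QTc itself. For PR, QRS or morphology the criterion carries no information.

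**Precision when no signal appears.** With zero cases among n, the two-sided exact 95% upper limit is 1 − 0.025^(1/n): 2.53% for n = 144 and 0.41% for n = 900. Two-sided limits are used because SAP section 3.1 specifies two-sided 95% intervals.

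**The case against.** The strongest reply is that section 10.7.2 simply supplies the definition of signal that section 8.3.6 omits: general wording in the assessments section, the operative criterion in the statistics section. On that reading there is no contradiction, only a term to define. The reading is possible, so the conflict is conditional. But section 8.3.6 speaks of the effect against placebo in general and of any signal. If QTc alone is meant, the mismatch with the other ECG endpoints remains and should be stated openly.

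Second, the separate ECG plan announced in SAP section 5.2.5 may settle the trigger, the thresholds and the population. That stands as a limit on this point, but the protocol would still carry two rules.

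Third, the other 1,008 subjects are not unobserved. Investigators review every automatic printout. Section 8.5.2 makes clinically significant ECG abnormalities reportable as adverse events, and after dosing these enter the by-arm TEAE analyses in SAP section 5.1. This stands. It does not cover values that cross a predefined threshold without being judged clinically significant.

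A reader might also infer that the contradiction itself cuts the abnormality endpoint from 900 exposed subjects to 144, so that the ECG objective could be declared clean on an inadequate sample. The documents do not support that. With no signal, both rules leave about 144 exposed; the 144-versus-900 comparison measures a deliberate and disclosed staged reading. The secondary ECG objective is framed as a double-delta comparison, and the subset is adequately powered for its QTc component. The rationale for 900 in section 10.1.1 concerns uncommon TEAEs, and nothing in the documents says ECG threshold values are uncommon.

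**Conclusion.** The point holds in a limited form. Sections 8.3.6 and 10.7.2 state different triggers and give opposite instructions in one identifiable case: the QTc criterion is met and another listed ECG endpoint shows a signal in the first 192. In that case the choice of section decides whether 1,008 subjects' ECGs are formally analysed. That is worth correcting before the analysis, because it changes what gets analysed and the correction is cheap.

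The small denominator for abnormality incidence is a separate matter of reporting. If no signal is found, the endpoint rests on about 144 exposed and 48 placebo subjects, and a finding of zero cases would exclude rates above about 2.5%, not 0.41%.

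This rests on three assumptions: signal in section 8.3.6 is not confined to QTc; the unseen ECG plan does not already resolve the rule; and 144 and 48 are expected counts. Incomplete blocks, the two definitions of the 192 and the treatment misallocation described in SAP section 3.4.4 could shift those counts.

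**What to change.** 1. Reconcile sections 8.3.6 and 10.7.2, and the separate ECG analysis plan, to one trigger for analysing the remaining ECGs. It should cover the placebo-corrected QTc bound and also the other listed ECG parameters, the predefined threshold abnormalities and the morphological findings in the first 192. If the sponsor intends a QTc-only trigger, the text should say so explicitly and justify it for the other endpoints.
2. Use one definition of the 192, with or without the Day 5 PK sample, in sections 8.3.4, 8.3.6 and 10.7.2.
3. Name the analysis population for abnormality incidence. If it stays on the subset, report the denominators and the exact interval, with a note that clinically significant findings in the other subjects are captured as adverse events.
4. Optional: if investigator-read Day 5 ECG results are already in the eCRF, tabulate them by arm for the Safety Set, labelled as automatic or investigator-read, and keep them out of the QTc claim. The documents do not show that these values are in the database, so this should not be required.

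Items 1 to 3 cost only wording, except that a broader trigger may call for manual reading of the stored ECGs more often than the QTc-only rule would. The sample size and the QTc analysis on the 192 do not change.

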## 10.8. Analysis of exploratory endpoints

#### Primary exploratory efficacy questions of interest

Because dermal trypanosomes could contribute as reservoirs to the transmission of g-HAT hampering the elimination goal, the primary exploratory question of interest is: Does acoziborole reduce the occurrence at 4 months of extravascular dermal *T.b. gambiense* in comparison with placebo?

#### Primary diagnostic parameter

A subject is considered positive to extravascular dermal *T.b. gambiense* if TgSGP-PCR test in skin is positive.

#### Primary estimand

The occurrence rate of positive extravascular dermal *T.b. gambiense* at 4 months based on the primary diagnostic parameters will be the primary measure of interest because the sample size is known and it corresponds to a measure of the level of potential transmission of reservoirs. The magnitude of the treatment effect will be the OR of positive dermal *T.b. gambiense*. As the OR is not easy to interpret when the rate of positive subjects in the placebo group is not small (P0 >0.05), the OR will be converted into the risk ratio (RR) using the following formula: RR = (P1/P0) = OR/[(1-P0) + (P0×OR)], where P1 and P0 are the estimated proportions of positive subjects in the acoziborole arm and placebo arm respectively. The ER (P1 – P0) will also be estimated as a secondary measure of the magnitude of the treatment as well as the NTT (number of subjects needed to treat to get one less positive subject at 4 months in acoziborole group).

#### Comparability of treatment group

To assess whether randomisation provided comparable treatment groups, randomised groups will be compared using descriptive statistics at baseline and more precisely the proportion of dermal trypanosome positive subjects at baseline.

#### Interpretability of results

The knowledge of the change of status between baseline and 4 months is helpful to interpret results. If in the placebo group, a large proportion of subjects change their status from negative to positive and positive to negative then the repeatability of the test result, and consequently the predictive validity of the diagnostic test, is questionable (see secondary analysis of the primary endpoint).

#### Primary statistical test

A Cochran-Mantel-Haenszel test using sites as strata will compare acoziborole and placebo occurrence rate at 4 months of positive dermal. The overall OR will be estimated for each parameter as well as the ERs and NTT.

In case of small proportions, the exact Cochran-Mantel-Haenszel test will be performed.

#### Generalisability of the treatment effect

The Breslow-Day test of homogeneity of the OR across sites will be performed to assess the generalisability of the treatment effect. If the test is significant, a forest plot will be provided to display the heterogeneity of the magnitude of treatment effect across sites and to detect sites explaining the heterogeneity.

#### Sensitivity analysis

The main sensitivity analysis will be performed on the subgroup of positive dermal trypanosome subjects at entry.

#### Handling of missing data

Missing data at month 4 will not be imputed to avoid loss of sensitivity of test (exploratory analysis of observed cases). However, a sensitivity analysis will assess the robustness of the primary analyses after imputation of a positive diagnosis in case of missing information.

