## 3. Study design and study design rationale

#### 3.1. Study design

This is a randomised, multicentre, double-blind, placebo-controlled, parallel-arm phase II/III study to assess the safety and tolerability of a single dose of acoziborole compared with placebo in adolescent and adult subjects seropositive to human African trypanosomiasis due to *T.b. gambiense* (g-HAT positive; not confirmed parasitologically [no demonstration of the parasite in any body fluid via microscopy]) in DRC and Guinea.

The double-blind, placebo-controlled nature of the study design will aid with minimising bias with the parallel-arm design allowing between subject comparison.

Subjects will be hospitalised at least 1 day before study treatment commences and will be randomised in a 3:1 ratio to acoziborole or matched placebo on Day 1 of the study. Following hospitalisation, subjects will attend follow-up visits at the study centre at 1- and 4-months post-treatment. At months 2 and 3, investigator contacts will be established between the site and subjects to ensure close follow-up of subjects and encourage study adherence. An on-site unscheduled visit will be proposed if deemed necessary by the investigator. Any subject with a positive parasitological test result during the study will end their participation in the study and be referred to the NSSCP for appropriate standard treatment.

In addition, a sub-study 'TrypSkin' to assess the presence of extravascular dermal *T.b. gambiense* in this population, will be proposed to subjects having given their consent to participate in the seropositive safety main study (in clinical sites participating in the sub-study only). Subjects can decide whether to participate or not in the sub-study independently of his/her participation in the main safety study.

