#### 8.3.2. Parasitology assessments

Assessments for presence of parasites using mAECT or mAECT-BC will be conducted during screening period, at Month 1, and at the EoS visit at Month 4. The most sensitive parasitological test (m-AECT-BC technique [16]) will be preferred to detect the presence of trypanosomes in blood. When indicated, lymph node aspirate will also be used to

microscopically detect the presence of trypanosomes.

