## 8.4. Exploratory assessments

For subjects participating in the TrypSkin exploratory sub-study, the following samples will be taken at screening (baseline) and 4 months (EoS):

- 3 mL fresh blood (in nucleic acid-preservative buffer) and 5 DBS
- Two 2 mm-skin-punch biopsies on the right back shoulder under local anaesthesia

Samples will be shipped to specialised partner laboratories (Institut National de Recherche Biomédicale [INRB], Institut Pasteur Guinea and Institut Pasteur Paris and Institute of Tropical Medicine [ITM] Antwerp) for the following analyses:

1- Molecular detection of trypanosomes:

- Common automatised extraction of total nucleic acids (TNAs) from fresh blood, DBS and skin biopsies
- On TNAs from fresh blood and skin (main validated diagnostic methods):
  - For all samples: TBR-PCR and 18S-PCR (*T. brucei s.l.*)
  - For TBR-PCR+ and/or 18S-PCR+ samples: T.b. gambiense-specific TgSGP-PCR
- On TNAs from fresh blood, DBS and skin (additional methods to be tested):
  - o qPCR detection using at least 2 targets
  - Multiplex RT-qPCR detection using novel targets
  - CRISPR-derived approach (SHERLOCK)
- 2- Immuno-histochemical detection of dermal trypanosomes:
  - At least 2 automatised IHC on Formalin-Fixed Paraffin-Embedded (FFPE) skin sections for all subjects with *T. brucei*-specific staining (Anti-Invariable Surface Glycoprotein 65 [ISG65] and Anti-cross reacting determinant [CRD] and secondary polymer amplification
  - Automatised acquisition and double *in silico* blind reading, pictures annotation and archiving
- 3- Preliminary tests for the detection of trypanosomes by Raman spectroscopy:
  - For each subject at each time point, one DBS from the field and one FFPE slide generated for IHC at IP Paris will be scanned by Raman spectroscopy at the University of Glasgow in the context of an exploratory procedure based on the measurements of biophysical parameters associated to the presence of trypanosomes.

• The results will not be uploaded in the central data base as the final analyses will rely on machine learning approaches after the end of the study.

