## 10.1.2. Ratio determination

Operational properties of various allocation ratios for the following assumptions are as follows:

- 1. Total sample size (for safety main study): n=1200 (900 acoziborole and 300 placebo)
- 2. Excess rate (ER) for safety: 1% (acoziborole = 2% of AEs of interest, Placebo = 1%)
- 3. Probability to detect an infrequent AE ( $\leq 1\%$  upper limit of class)
- 4. Probability to detect an infrequent AE (0.5% mid-class)

5. Total sample size for efficacy (TrypSkin exploratory sub-study): n=725 in order to ensure a minimum of 700 evaluable biopsies

6. Binary endpoint for efficacy: success=no tryps detected in punch skin at month 4, failure = at least one tryp-positive result in punch skin at Month 4

7. Probability to detect at least one trypanosome in derma at baseline: 20%

8. No effect of placebo on occurrence of tryps in derma at month 4: failure rate at 4 months=20%

9. Effect of 95% of acoziborole on occurrence of tryps in derma at Month 4 (efficacy): failure rate at Month 4 =  $0.05 \times 0.20 = 0.01$  or 1%

10. Excess rate of success in acoziborole group: 19% (assuming the same efficacy as stage 2 patients)

	Safety			Efficacy (for TrypSkin sub-study)		
Allocation ratio	Sample size for safety	Exact 95% CI limits of ER	Probability to detect an infrequent AE if occurrence rate = 1% (upper limit), = 0.5% (mid-class) and = 0.1% (lower limit of class)	Sample size for efficacy	Exact 95% CI limits of ER Estimate = 20%	Power (chance to detect a difference vs PBO) if acoziborole efficacy is 95%
3:1	PBO = 300 ACO = 900	Lower = -0.92% Upper = +2.41%	Upper: 99.99% Mid: 99.90% Lower: 59.36%	PBO = 175 ACO = 525	Lower = 13.38% Upper = 25.55%	99.99%
2:1	PBO = 400 ACO = 800	Lower = -0.64 Upper = +2.42%	Upper: 99.96% Mid: 98.18% Lower: 55.06%	PBO = 233 ACO = 467	Lower =14.02% Upper = 24.62%	99.99%
3:2	PBO = 480 ACO = 720	Lower = -2.30%* Upper = +0.66%*	Upper: 99.93% Mid: 97.29% Lower: 51.34%	PBO = 280 ACO = 420	Lower = 14.51% Upper = 24.15%	99.99%
1:1	PBO = 600 ACO = 600	Lower = -0.44% Upper = +2.51%	Upper: 99.75% Mid: 95.06% Lower: 45.23%	PBO = 350 ACO = 350	Lower: 14.81% Upper: 23.48%	99.99%

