## 10.10. Missing, unused, and spurious data

Missing data will not be imputed. An observed case approach will be used for the analyses, which will include subjects with available data for a given parameter.

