5.3.2. Sensitivity Efficacy (sub-group) analysis

The secondary set of subjects for exploratory efficacy is the set of all seropositive subjects who were positive for the presence of trypanosome (*Tb spp.*) by at least one method in skin, blood and/or DBS at baseline. The analysis will be repeated considering type of sample skin, blood or DBS separately. Secondary diagnostic parameters are occurrence of positive results by IHC in skin, by TBR-PCR, 18S-PCR in skin, blood and/or DBS, as well as by any novel diagnostic parameters corresponding to occurrence of positive results by multiplex qPCRs, multiplex RT-qPCRs and/or SHERLOCK in skin, blood and/or DBS. The secondary analyses will be the same as the primary

diagnostic analysis, as the main sensitivity analysis will be performed on the subgroup of positive dermal trypanosome subjects at entry (Secondary exploratory diagnostic Analysis). Missing data at month 4 will not be imputed to avoid loss of sensitivity of test (exploratory analysis of observed cases). However, a sensitivity analysis will assess the robustness of the primary analyses after imputation of a failure (positive diagnosis and presence of symptoms accordingly) in case of missing information.

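### The TrypSkin Month 4 skin analysis has no rule for subjects who leave with confirmed parasites before Month 4, and its only missing-data check codes every missing result as positive

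*Protocol*

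**What the plan says.** Four provisions meet at this point.

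- **Exit rule.** Protocol 3.1: "Any subject with a positive parasitological test result during the study will end their participation in the study". Protocol section 8 and SAP 2.1 repeat it.
- **Timing.** Parasitology "will be conducted during screening period, at Month 1, and at the EoS visit at Month 4" (Protocol 8.3.2), and an unscheduled visit is possible. For the sub-study, "the following samples will be taken at screening (baseline) and 4 months (EoS" (Protocol 8.4). The schedule of events lists no biopsy at early exit.
- **Main analysis.** Protocol 10.8, Handling of missing data: "Missing data at month 4 will not be imputed to avoid loss of sensitivity of test (exploratory analysis of observed cases". Protocol 10.10 sets the same rule generally: "Missing data will not be imputed. An observed case approach will be used for the analyses".
- **Missing-data check.** The same paragraph of Protocol 10.8 adds that "a sensitivity analysis will assess the robustness of the primary analyses after imputation of a positive diagnosis in case of missing information". SAP 5.3.2 keeps the rule and extends it to symptoms: "after imputation of a failure (positive diagnosis and presence of symptoms accordingly) in case of missing information".

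The effect measure is the odds ratio (OR). The risk ratio (RR), excess rate (ER) and number needed to treat are derived alongside it. Conversion to parasite-positive is tabulated by arm elsewhere (Protocol 10.7.1, SAP 5.1), but nothing says how such a subject counts for the skin endpoint.

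**The concern.** A subject confirmed before the Month 4 visit has no Month 4 skin result because of the infection under study. The observed-case analysis treats that loss like a spoiled sample or a missed visit. If acoziborole works, such exits might be expected more often on placebo, so failures would be removed from the arm that should have most of them.

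The check errs the other way. It counts the confirmed exits as failures, but it does the same to a subject who was skin-negative at baseline and simply missed the visit. Few true positives are expected on acoziborole (1% at the planned prevalence), so even a small missing fraction can make up most of that arm's positives.

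Neither analysis separates infection-driven exits from unrelated missing data. The pair may therefore fail to show whether the result is robust to missing data.

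**Working it through.** **Inputs from the documents.** 175 placebo and 525 acoziborole subjects (ratio tables, Protocol 10.1.2 and SAP 2.4.3). Placebo: "No effect of placebo on occurrence of tryps in derma at month 4: failure rate at 4 months=20" percent. Acoziborole: 0.05 × 20% = 1%. Two-sided 5% level (SAP 3.1). The sub-study stops if baseline positivity by any method in any sample is below 2% (Protocol 10.9).

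**Assumptions.** The missing rate m is not given. I use 1% to 5%, equal in both arms. The upper value borrows the 5% provision for non-analysable skin samples in Protocol 10.1.1; Protocol 9.2 calls loss to follow-up low without giving a rate. The share of failures leaving before Month 4 is not given either; I use 10% to 50%.

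**Step 1: the plan's own figure.** 20% against 1% with 175 and 525 subjects gives power 0.9999996 (normal approximation) or 0.9999998 (Fisher). The stated 99.99% reproduces. RR = 0.05, OR = 0.0404, ER = 19.0 points in favour of acoziborole.

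**Step 2: observed cases.** Let shares x (placebo) and y (drug) of failures exit early. The rates become 0.20(1−x)/(1−0.20x) and 0.01(1−y)/(1−0.01y). Each arm's odds are multiplied by one minus its exit share, so OR′ = 0.0404 × (1−y)/(1−x).

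| x, y | Placebo rate | ER (points) | OR |
|---|---|---|---|
| 10%, 10% | 18.4% | 17.5 | 0.0404 |
| 25%, 25% | 15.8% | 15.0 | 0.0404 |
| 50%, 50% | 11.1% | 10.6 | 0.0404 |
| 10%, 0 | 18.4% | 17.4 | 0.045 |
| 25%, 0 | 15.8% | 14.8 | 0.054 |
| 50%, 0 | 11.1% | 10.1 | 0.081 |

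Rates and ER shrink in every row. The OR moves only when exit shares differ by arm. Power is at least 99.6% throughout.

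**Step 3: every missing result coded positive.** Each arm's rate becomes q = m + (1−m)p. z = (q0 − q1)/√[q̄(1−q̄)(1/175 + 1/525)], with q̄ the pooled rate.

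| Prevalence | m | Placebo | Drug | ER (points) | RR | OR | z | Power |
|---|---|---|---|---|---|---|---|---|
| 20% | 0 | 20.0% | 1.0% | 19.0 | 0.05 | 0.040 | 9.35 | >99.99% |
| 20% | 1% | 20.8% | 2.0% | 18.8 | 0.10 | 0.077 | 8.62 | >99.99% |
| 20% | 5% | 24.0% | 5.95% | 18.05 | 0.25 | 0.20 | 6.76 | 99.99% |
| 10% | 5% | 14.5% | 5.5% | 9.0 | 0.38 | 0.34 | 3.87 | 94% |
| 5% | 0 | 5.0% | 0.25% | 4.75 | 0.05 | 0.048 | 4.57 | 95% |
| 5% | 5% | 9.75% | 5.2% | 4.5 | 0.54 | 0.51 | 2.12 | 55% |
| 2% | 0 | 2.0% | 0.1% | 1.9 | 0.05 | 0.049 | 2.88 | 72% |
| 2% | 1% | 3.0% | 1.1% | 1.9 | 0.37 | 0.36 | 1.73 | 43% |
| 2% | 5% | 6.9% | 5.1% | 1.8 | 0.74 | 0.72 | 0.90 | 16% |

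At m = 5% the drug arm has 525 × 0.05 = 26.25 imputed positives. Observed positives there are 525 × 0.95 × 0.01 = 5.0 at 20% prevalence and 0.5 at 2%. At m = 1% and 20% prevalence the counts are about 5.2 and 5.2.

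**Step 4: filling unrelated missing results from baseline.** If placebo status does not change, as the plan assumes, the placebo rate stays at p. The drug rate becomes 0.05p(1−m) + mp, so RR = 0.05(1−m) + m at any prevalence. That is 0.0595 at m = 1% and 0.0975 at m = 5%. At 2% prevalence and m = 5% the rates are 2.0% and 0.195%, and z = 2.58, against 2.88 with complete data.

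**The case against.** The strongest defence is that observed cases plus missing-as-failure is a conventional main analysis with a conservative bound, and that the bound already counts confirmed exits as failures. The sub-study is exploratory throughout. At the planned 20% prevalence the bound still succeeds easily. This stands as far as it goes, but both analyses treat all reasons for missingness alike, so the pair cannot show which kind drives a difference between them.

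A reader might infer that the main OR is biased toward no effect. The documents do not establish that. Step 2 shows the OR unchanged when exit shares are equal. Only exits before Month 4 lose the biopsy, since a subject confirmed at Month 4 is at the visit where it is scheduled. No number or expected rate of early exits is given.

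A reader might also infer that the check will overturn a real effect. At 20% prevalence ER moves only from 19.0 to 18.05 points and z is 6.76. Significance comes under pressure only at roughly 2–5% prevalence, where at 2% the main analysis itself has just 72% power (59% by Fisher). That range remains within the plan: the 2% stopping rule counts any method in any sample, while the primary endpoint is TgSGP-PCR in skin alone.

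It is also fair that microscopic confirmation in blood or lymph is not the skin endpoint. Protocol 10.8 itself says current specific molecular methods have low sensitivity, so a confirmed subject need not test skin-positive.

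Finally, the baseline-positive subgroup analysis in Protocol 10.8 does exclude baseline-negative subjects. It changes the population, however, and does not address missing data.

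**Conclusion.** The point holds in limited form, as a cheap improvement to an exploratory analysis. The observed-case rule silently drops subjects confirmed before Month 4. That lowers the occurrence rates and ER, and attenuates the OR if early exits are a larger share of failures on placebo. How far this matters cannot be said without a count.

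The all-positive check inflates the RR from 0.05 to 0.10–0.25 at 20% prevalence and to 0.37–0.74 at 2%, for 1–5% missing. It distorts RR and OR at every prevalence examined. It leaves the ER and the test conclusion essentially intact at 20%, and it is uninformative on significance at about 2%.

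These sizes rest on 95% efficacy, arms of 175 and 525, and missing rates that are equal in both arms and unrelated to infection. Treating early exits as lost failures further assumes that they would have been skin-positive.

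**What to change.** In Protocol 10.8 (Handling of missing data) and SAP 5.3.2:

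1. Add an analysis that counts an exit for confirmed parasites before the Month 4 visit as a failure, and fills any other missing Month 4 skin result with the subject's own baseline skin result.
2. Keep all-missing-positive, labelled as an extreme bound.
3. Tabulate the reasons for missing Month 4 skin results by arm, with confirmed exits before Month 4 as a separate row.

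Multiple imputation using baseline result, arm and site is optional; with an expected 0.5 to 5 positives on acoziborole it may be unstable.

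The cost is a few lines of text and modest programming on data already collected. The downside is that a blood- or lymph-confirmed exit counts as a failure without a skin TgSGP-PCR result, so the added analysis uses a composite outcome and must state that assumption. Filling from baseline is itself conservative for acoziborole, as Step 4 shows, because it gives a treated subject with a missing result no credit for clearance.
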